Study Design Overview: We propose to study the separate and combined effects of the FDA-approved cannabinoid dronabinol (Marinol) and the prototypical opioid hydromorphone (Dilaudid). Following telephone and screening to establish study eligibility, a cohort of **n=100** adults with knee osteoarthritis (KOA) will complete four different within-subject experimental sessions. Participants will complete one of two Phases, receiving either a 4mg or 2mg dose of hydromorphone. Randomization will be split equally across the two Phases. During each session, participants will complete baseline QST, questionnaires, and a neurocognitive battery. Oral hydromorphone will be administered in the first session. Subsequent sessions will consist of 1 of 3 conditions, and session order will be randomized and counter-balanced. Conditions will be 1) placebo; 2) oral dronabinol (10mg); and 3) combined hydromorphone and dronabinol (10mg). Measures will be repeated throughout the session to fully characterize the drug effects. Participants and staff will be kept blinded to the study medications under investigation, and participants will be informed in the consent form they may receive a combination of FDA-approved stimulants, benzodiazepines, opioids, cannabinoids, over-the-counter medications or placebo, though the participants will not actually be receiving stimulants, benzodiazepines, or over-the-counter drugs. All participants will be provided with transportation to and from the experimental sessions. Primary outcomes are measures of clinical pain, central sensitization, physical function and drug effects/adverse events. A subset of participants will undergo blood draws for pharmacokinetic (pK) profile. This will be voluntary and should aid recruitment as those that do not want an IV will still be allowed to participate in the study. We will aim to recruit 30 participants that volunteer to undergo IV/blood drawing procedures in order to characterize pK.

Phase 1: The initial Phase of this project will include hydromorphone at a dose of 4mg.

Phase 2: The second Phase of this project will include hydromorphone at a dose of 2mg in order to evaluate drug effects at a reduced opioid dose.

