| Randomized Order | | |
| 2 | 0 (placebo) | 0 (placebo) |
| 3 | 0 (placebo) | 10mg |
| 4 | 4mg | 10mg |

approximately 0930 participants will complete baseline QST, physical functioning measures, and self-report measures (see below). The second 10-14mL blood draw (for those in the pK group) will be collected and then two oral capsules containing either active drug or placebo (randomized in sessions 2-4) will be administered at approximately 1100. Briefly, subjects will complete QST, physical functioning, cognitive testing, self-report, and vital sign measures (as well as blood draws for those in the pK group) at regular intervals following study drug administration. Self-report measures will include specific opioid agonist and antagonist effects, to assess whether cannabinoids

are exerting an effect on a particular category of opioid agonist symptom, and will capture whether any negative effects (e.g., nausea) occur. Frequent collection will enable evaluation of time to peak drug effects, duration of effects, and general time course of effects and is a widely used and accepted approach in laboratory studies of drug effects. During the final assessment each day, subjects will complete a Drug vs. Money Questionnaire to indicate the dollar value they would place upon the drug received⁹⁸, which is a well-accepted proxy measure of abuse liability. Study staff will document adverse events throughout the study and any subject who experiences a strongly unpleasant effect of the medications, or wishes to discontinue for any reason will be able to end participation at any time. Any subject who is experiencing strong agonist effects at the end of the session will be provided overnight accommodation in the Clinical Research Unit (CRU; which is located on our campus and with whom we have frequent collaborations); based on our experience we expect this to be rare and are budgeting for 20% of sessions to undergo a one-night CRU stay.

Measures

Pilot testing indicates it takes approximately one hour to complete the assessment battery (see Table 2).

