c. Opioid-Cannabinoid Interactions: There are limited data available to indicate whether there are consistent opioid-cannabinoid interactions on physiological outcomes. One study that was published in 1975 evaluated combinations of delta-9 THC (which is present in smoked marijuana and dronabinol) and the opioid oxymorphone reported that the combination of drugs decreased CO₂ slope and increased tachycardia, though heart rate increased generally following exposure to delta-9 THC¹⁴¹. A second, more recently published study reported that a 40mg dose dronabinol that was administered to participants undergoing opioid withdrawal (as a method of minimizing the withdrawal syndrome) also produced tachycardia¹⁴². This effect was eliminated once the dose of dronabinol was reduced to 30mg. We do not believe this will be a problem for this study. The second study only reported negative effects when dronabinol was administered at the highest dose approved for human consumption by the FDA (40mg) and the effect was completely eliminated once the dose was marginally reduced. In addition, this study enrolled patients who were opioid dependent and withdrawing from opioids, and increases in heart rate and blood pressure are well-recognized symptoms of the opioid withdrawal syndrome. Thus, though we have presented these studies to be transparent, we do not believe their results will necessarily generalize to our patient population. We have listed our protections against risk in the following section.

d. Chance That Participants May Begin Abusing Opioids or Cannabinoids Following Exposure to Study Drugs: There is a small but potential risk that exposing non-drug abusing individuals to doses of hydromorphone or cannabinoids may elicit reinforcing effects that could precipitate subsequent drug-use behavior. Enrolling non-drug users into controlled laboratory studies is a conventional strategy that has been used extensively to evaluate the abuse liability potential of numerous drugs of abuse both within our laboratory and by other laboratories.

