a. Protection Against Hydromorphone Risks: We have extensive experience in the administration of hydromorphone and other opioid agonists in controlled laboratory settings and therefore anticipate few problems. Any individual who may be prone to the risks associated with hydromorphone will be excluded from participating. Although research staff and participants will be blinded to the exact medication provided, both groups will be informed of the potential side effects and risks associated with the study drug administration. Participants will be free to discontinue study participation at any time without consequence. The dose of hydromorphone that is being administered is consistent with clinical care, and is a medium level dose for the treatment of pain. Hydromorphone will always be administered along with placebo in the first session, which will provide a valuable opportunity to exclude from further participation any participant who experiences untoward effects (e.g., nausea, vomiting) resulting from that dose of hydromorphone. Great care has been taken in selecting the appropriate drug doses to ensure hydromorphone is well-tolerated and safe for our participants and participants will also be able to discontinue study participation at any time. The most serious risk associated with hydromorphone administration is respiratory depression. We believe this risk is minimal in this study for several reasons. First, we are administering a mid-level dose and have

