b. Protection Against Dronabinol Risks: The majority of risks that are known to occur following dronabinol administration are psychiatric in nature. These risks are recognized as being transient and readily reversible. To mitigate these risks, we will exclude participants who endorse having previously experienced negative effects to cannabinoid products. We will also conduct psychiatric screening during the Screening session to ensure that patients with current or history of psychiatric events are excluded from study participation. Further, all participants will be informed about the potential side effects of the study medications and will be permitted to end study participation at any time if they experience negative events, with no consequences. Finally, we are providing participants with taxi service to and from the study sessions to ensure no persistent drug effects will impact their driving. We are also budgeting for the potential for a participant to stay the night at the CRU following study drug exposure. Based on our previous experience, we expect this to be a rare occurrence but are prepared to make that option available as needed.

To protect against risks of increased heart rate and tachycardia following co-administration of opioids and cannabinoids we will require all participants to be in good cardiovascular health prior to study enrollment (evidenced by a clean ECG, reviewed by a study physician). During sessions, all participants will be attached to a vital signs monitor and will have vital signs collected at 15 minute intervals for the first 2 hours to ensure safety. The risk of an opioid/cannabinoid interaction will only occur during a single study session, however since staff and participants will be blind as to the timing of that session, we will employ this monitoring schedule for all sessions. We will review data following completion of 5 participants and if it becomes evident that tachycardia is occurring regularly during any sessions, we will reevaluate the dose of study drugs being administered. However we believe that any changes to our dosing strategy are highly unlikely and this monitoring schedule will ensure participant safety during study participation.

c. Protection Against Risks That Participants May Begin Abusing Opioids or Cannabinoids

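### The only stated study-level dose review is one look timed by five completions with tachycardia as its sole named signal, so early stopping delays it and no respiratory signal is listed

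*Combined protocol and SAP*

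**What the plan says.** Section 8.b, Protection Against Dronabinol Risks, states: "We will review data following completion of 5 participants and if it becomes evident that tachycardia is occurring regularly during any sessions", then "we will reevaluate the dose of study drugs being administered". No other sentence in the document plans a re-evaluation of the study doses. The word *regularly* is not defined for this review, and no repeat is mentioned. Section 7.c has interim analysis in its heading, but no interim plan follows.

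The same paragraph of Section 8.b notes: "The risk of an opioid/cannabinoid interaction will only occur during a single study session". Under Study Design Overview (Section 4.a), hydromorphone alone comes first, and for the other three conditions "session order will be randomized and counter-balanced". The combination can therefore fall in session 2, 3 or 4. Under Experimental Sessions, a participant who has a strongly unpleasant drug effect or "wishes to discontinue for any reason will be able to end participation at any time".

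On respiration:

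- Section 8.a, Opioid-Cannabinoid Interactions, cites a study of THC with an opioid that found a decreased CO2 "slope and increased tachycardia, though heart rate increased generally following exposure to delta-9 THC".
- Section 8.b, Protection Against Hydromorphone Risks, says: "The most serious risk associated with hydromorphone administration is respiratory depression". It then sets out steps for a respiratory rate under 12 per minute with sedation and for oxygen saturation under 90%. These steps concern the affected participant only.

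**The concern.** The protocol gives this review the role of deciding whether the doses need another look, and most of a planned cohort of 100 comes after it. Two features work against that role.

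First, the clock runs on completions. The review is meant to detect a problem that can arise only in the combination session, yet a participant who receives the combination and then leaves does not move the review closer. If the combination is poorly tolerated, more people are exposed before the review takes place.

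Second, the signals named for the review are narrower than the risks the protocol describes. Its own background reports both a respiratory effect and tachycardia for a THC-opioid combination, but only tachycardia is carried into the review. A respiratory pattern spread over several participants would be handled person by person, with no stated route to a decision about the study dose.

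**Working it through.** The document gives no derivation for the figure of five and no event rate, so there is no planned figure to reproduce. The checks below show what a look of this size and timing can do. All rates are assumptions.

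**Inputs.** Five completions prompt the review (Section 8.b). Each completer has one combination session (Section 8.b), so five completers supply five combination sessions.

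**1. What five combination sessions can show.** For a true rate p on the combination:

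- P(no case) = (1 − p)^5
- P(at least 2 cases) = 1 − (1 − p)^5 − 5p(1 − p)^4, which is one possible reading of *regularly*

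| p | No case | At least 2 cases |
|---|---|---|
| 10% | 0.9^5 = 59% | 8% |
| 20% | 0.8^5 = 33% | 26% |
| 30% | 0.7^5 = 17% | 47% |
| 50% | 0.5^5 = 3% | 81% |

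After 0 of 5, the one-sided 95% upper limit is 1 − 0.05^(1/5) = 0.451, or 45%.

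**2. How early stopping moves the clock.** Let s be the probability that a participant stops because of the combination before completing, and assume no other dropout. The mean number of such people before the fifth completer is 5s/(1 − s). The chance of at least one is 1 − (1 − s)^5.

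| s | Mean number | At least one |
|---|---|---|
| 10% | 0.5/0.9 = 0.6 | 41% |
| 20% | 1.0/0.8 = 1.25 | 67% |
| 30% | 1.5/0.7 = 2.1 | 83% |

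With counterbalanced order, about one third receive the combination last and have no later session to skip. If 30% of the others would leave after the combination, and nobody leaves mid-session, then s = 0.30 × 2/3 = 20%, and the middle row applies.

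**3. Signals, set side by side.**

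| Section | Respiratory content | Linked to the dose review? |
|---|---|---|
| 8.a, Opioid-Cannabinoid Interactions | Decreased CO2 slope with a THC-opioid combination | No |
| 8.b, Protection Against Hydromorphone Risks | Most serious hydromorphone risk; rate and saturation events defined | No |
| 7.d, Early stopping rules | None; blood pressure and heart rate prompt a physician consult | No |
| 8.b, Protection Against Dronabinol Risks | None; tachycardia only | This is the review |

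**4. Phases.** Study Design Overview calls 4 mg the initial Phase and 2 mg the second, but also says that randomization is split equally across them. If the Phases run in sequence, the first five completers all received 4 mg, and no review is stated for 2 mg. If they run together, the five are divided between the doses. The text does not settle which applies.

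**The case against.** The strongest reply is that the sentence fixes when the review happens and not whose data enter it. Its criterion covers any sessions, so data from people who stopped may well be included. That stands. A reader might infer that only completers are examined and that the combination would therefore look better tolerated than it is. The document does not state such an exclusion, nor how often a person with tachycardia would leave, so no bias can be claimed or given a size. Only the delay follows from the text.

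A reader might also infer that respiratory findings are barred from prompting a dose review, or that a second review is ruled out. Neither is written. What the text supports is that no respiratory criterion and no repeat are stated.

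The individual safeguards are real. Section 7.d has physician-consult thresholds. Section 8.b has vital signs every 15 minutes for the first two hours in every session, and respiratory steps with oxygen and naloxone available. Section 8.c has adverse event reporting. Hydromorphone alone always comes first, so people who react badly to it can be excluded before the combination. Section 7.d names cardiovascular risk as the largest, which explains why tachycardia is the listed signal. It does not explain leaving out the respiratory finding from the combination study that the protocol itself cites, and none of these safeguards is tied to a study-level dose decision.

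Finally, the rule looks for a regular event and not a first case, and five completers supply 5 × 2 = 10 dronabinol sessions. A very frequent event would probably be noticed: at 50%, two or more cases appear in the five combination sessions with probability 81%. This is fair, but the sessions with dronabinol alone do not inform on an interaction with the opioid, and at 30% two or more cases appear less than half the time (47%).

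**Conclusion.** The concern holds in a limited form. The single stated dose review is timed by completions, so people who stop after the combination do not advance it and poorer tolerability delays it. Whether their data are reviewed is not stated. Tachycardia is the only named signal, although the protocol's own risk sections give grounds for respiratory events to be considered as well.

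The look is small. For assumed rates of 10% to 30% on the combination, the chance of seeing no case in five combination sessions runs from 59% down to 17%, and a clean result remains compatible with a rate up to 45% (one-sided 95%). The delay is modest: on average 0.6 to 2.1 additional people exposed, if 10% to 30% stop because of the combination before completing. These figures rest on assumed rates, independence between participants and, for the delay, no other dropout. The points about timing and signals rest on the text alone.

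**What to change.** Amend the review sentence in Section 8.b as follows:

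- Time the review by the first five participants who have received the combination session, whether or not they go on to complete.
- State that data from everyone dosed by then are reviewed, including those who stopped.
- Reconcile the sentence with Section 8.a (Opioid-Cannabinoid Interactions) and Section 8.b (Protection Against Hydromorphone Risks) by listing the respiratory-rate and saturation events already monitored alongside heart rate.
- State whether the review also applies to the other Phase.

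The meaning of *regularly*, any thresholds and any dose action are for the study physicians to set. Nothing here proposes a dose or a clinical limit. The review can stay blinded, because the criterion already covers any sessions.

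The cost is slightly more protocol wording and a few short listings from data already collected. The change does not enlarge the look, so the limits of five combination sessions shown above remain.
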